4.6.7 Study Medication Administration and Compliance

Study drug exposure will be summarized by treatment group using descriptive statistics for each time point and overall.

Overall study drug compliance will be calculated as the number of doses assumed to be taken relative to scheduled dosing period as follows:

$$\text{Compliance (\%)} = \frac{(\# \text{ Capsules of total dispensed} - \# \text{ Capsules of total returned})}{(\text{last dose date} - \text{first dose date} + 1) \times 4 \text{ capsules/day}} \times 100$$

Overall percent compliance will be calculated per patient in the ITT and mITT populations and summarized by treatment group using descriptive statistics.

4.6.8 Discontinuation of Study Drug

A Kaplan-Meier analysis of the time to premature discontinuation of study drug will be presented by treatment arm. A temporary discontinuation followed by re-starting study drug will not be considered a discontinuation in this analysis. Event probabilities at 6-month intervals and the median time to event (if estimable) will be presented. The log-rank test will be used to compare treatment groups.

4.6.9 Early Termination from the Study

A Kaplan-Meier analysis of the time to early termination will be presented by treatment arm. The date of termination for patients who do not complete the study due to any reason besides death will be used as the event date. Patients who do not terminate early or who terminate due to death will be censored at the date of death or last contact. Event probabilities at 6-month intervals and the median time to event (if estimable) will be presented. The log-rank test will be used to compare treatment groups.

4.6.10 Medications of Special Interest

At each scheduled visit (on site or by phone contact), information on changes in ezetimibe, statins, angiotensin-converting enzyme (ACE) inhibitors/angiotensin receptor blockers (ARBs)/beta blockers, and anti-diabetic drugs will be collected. For each medication type, the number and percentage of patients who started a new medication, discontinued a medication, increased the dose or decreased the dose of a medication will be presented by visit/phone contact. The overall number of patients with at least one of the above changes during the study will also be summarized by medication type.

4.6.11 Prior and Concomitant Medications

Non-study medications will be coded using the latest available version prior to database lock of the World Health Organization Drug Dictionary (WHO-DRUG) and the Anatomical Therapeutic Chemical (ATC) classification system. Coding includes the anatomical main group (ATC 1st Level), therapeutic class (ATC 3rd Level), and preferred term. All verbatim descriptions and coded terms will be listed for all non-study medications.

Prior medications are defined as non-study medications with a stop date before the randomization date.

Concomitant medications are defined as non-study medications with a stop date on or after the date of randomization. Medications that started prior to randomization but continued during study will also be defined as concomitant. Ongoing medications without stop dates are considered concomitant.

Medications with partial onset/stop dates that indicate that the medication could be concomitant in relation to the date of randomization are classified as concomitant. Otherwise, they are classified as prior medications.

The numbers and percentages of patients in each treatment group taking concomitant medications will be summarized by ATC therapeutic class and preferred term. For each patient, multiple records of the same concomitant medication will be counted only once within each therapeutic class and preferred term.

Listings will be provided for both prior and concomitant medications.

4.7 Efficacy Analyses

4.7.1 Primary Efficacy Endpoint

4.7.1.1 Primary Analysis

The primary efficacy endpoint is the time from randomization to the first occurrence of any component of the composite of the following adjudicated clinical events:

- CV death,
- Nonfatal MI (including silent MI; ECGs will be performed annually for the detection of silent MIs),
- Nonfatal stroke,
- Coronary revascularization,
- Unstable angina determined to be caused by myocardial ischemia by invasive/non-invasive testing and requiring emergent hospitalization.

All observed data that are positively adjudicated by the CEC, including data after discontinuation of study treatment for patients who discontinue study drug prematurely, will be included in the primary analysis.

Suspected endpoint events are adjudicated by the CEC without knowledge of the treatment. Counts and Kaplan-Meier estimates of the percentage of patients experiencing each type of adjudicated event by study completion, along with overall counts for each type, will be presented by treatment arm. A separate table of the number of events that are ruled out by the CEC will also be displayed.

The event time will be calculated as the (date of first event – date of randomization + 1 day) for patients who experience one or more of the primary endpoint events. The following provides detailed considerations for determining the date of event/date of censoring:

- Patients who do not experience a primary efficacy event prior to the end of the study or withdrawal from the study early without a preceding primary efficacy event will be censored at the date of their last visit/phone contact.
- Patients who die with an adjudicated undetermined cause of death and without a preceding endpoint event will be considered to have an adjudicated CV death and this will be included as an event in the primary analysis.

- In view of the 90-day monitoring period for CV events, patients who have a non-CV death within 90 days of last contact without having had an earlier CV event will be censored at the time of death. Patients who have a non-CV death more than 90 days after last contact without having had an earlier CV event will be censored at the date of their last visit/phone contact.
- The primary analysis of silent MI will assume that all silent MIs occurred on the date of the first tracing indicative of a silent MI.

Kaplan-Meier estimates will be used to summarize the time to the first event of the composite endpoint. Event probabilities at 6-month intervals and the median time to event (if estimable) will be presented. The log-rank test, stratified by stratification variables at randomization (CV risk category, use of ezetimibe, and geographical region [Westernized, Eastern European, and Asia Pacific countries]), will be used to compare the time-to-event between treatment groups. The two-sided alpha level for the primary analysis will be reduced from 0.05 to account for the interim analyses based on a group sequential design with O'Brien-Fleming boundaries generated using the Lan-DeMets alpha-spending function.

The hazard ratio (HR) comparing the two treatment groups along with a confidence interval (CI) adjusted for the interim analyses and p-value will be calculated from a stratified Cox proportional hazards (PH) model with treatment as the only covariate, and stratified by CV risk category at baseline, use of ezetimibe at baseline, and geographical region (Westernized, Eastern European, and Asia Pacific countries). Kaplan-Meier curves stratified by each of the stratification variables will be presented.

The primary efficacy analysis will be performed on the ITT population. A corresponding sensitivity analysis will be performed using the mITT and PP populations.

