3.2 Study Design

This is a Phase 3b, multi-center, multi-national, prospective, randomized, double-blind, placebo-controlled, parallel-group study.

This is an event driven trial comparing the effect of AMR101 vs. control, in terms of the composite endpoint listed above as the primary efficacy endpoint. The study has been planned to accrue a total of 1612 efficacy endpoint events with two planned interim analyses when approximately 967 (60%) and 1290 (80%) of the events have occurred and been adjudicated. The study includes patients with established CVD (CV Risk Category 1) and patients ≥ 50 years old with diabetes and at least one additional risk factor for CVD but with CVD not established (CV Risk Category 2).

Sample size calculation was based on assumptions of constant hazard, asymmetric recruitment rate over time and without factoring for dropouts. A risk reduction corresponding to a hazard ratio of 0.85 (AMR101 vs. control) is assumed. 1612 events would be required to detect this hazard ratio with approximately 90% power with one-sided alpha-level at 2.5% and with two interim analyses.

The recruitment period is assumed to be approximately 4.2 years with 20% recruitment in the first year, 40% in the second year, 20% in the third year, 19% in the fourth year and the remaining 1% in the last 0.2 years. The expected maximum study duration is estimated at 6.5 years unless the trial is terminated early for efficacy or safety issues. A one-year event rate of 5.2% (hazard = 0.053) in the control arm is also assumed. Under these assumptions the number of patients to be enrolled is $N = 7990$.

Randomized treatment assignment to either 4 g/day AMR101 or placebo in a 1:1 ratio will be provided using the internet via an interactive web response system (IWRS). Randomization will be stratified by CV Risk Category 1 or 2 (defined in the inclusion criteria of the study protocol), use of ezetimibe, and by geographical region (Westernized, Eastern European, and Asia Pacific countries).

Approximately 70% of randomized patients will be in CV Risk Category 1, and approximately 30% of randomized patients will be in CV Risk Category 2. Enrollment of patients within a CV risk category will be stopped when the planned number of patients in that risk category is reached or, if the enrollment target is extended beyond 7990 patients (as

described in Section 4.1), then only CV Risk Category 1 will be included in further enrollment.

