4.7.2 Components of Primary Endpoint

The time to first occurrence of each of the five component events of the primary endpoint will be analyzed by the same methods described for the primary endpoint. Kaplan-Meier

estimates, the log-rank test stratified by stratification factors used at randomization, and the Cox proportional hazards model including the stratification factors as specified above for the primary efficacy endpoint, will be summarized by treatment group. Kaplan-Meier curves stratified by each stratification factor will be presented. These analyses will be conducted for the ITT, mITT and PP populations.

Similarly, the rules for determining date of event/date of censoring for the primary efficacy endpoint (Section 4.7.1) will be applied to the components of primary endpoints. For the CV death endpoint, patients who do not die from CV causes will be censored at death from non-CV causes or last visit/phone contact as described in Section 4.7.1.1. For all other events (nonfatal MI [including silent MI], nonfatal stroke, coronary revascularization, and hospitalization for unstable angina determined to be caused by myocardial ischemia by invasive/non-invasive testing), patients who do not experience the event will be censored at death or last visit/phone contact, consistent with that described in Section 4.7.1.1.

In addition, a recurrent event analysis using Andersen-Gill and Li-Lagakos methods will be carried out for the individual primary event constituents other than CV death.

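### The Kaplan-Meier event percentages in the SAP censor deaths that preclude the event, so they overstate the share of patients affected in each arm; the tests are untouched

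*Combined protocol and SAP*

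**What the plan says.** SAP 4.7.1.1 promises, by arm, "Counts and Kaplan-Meier estimates of the percentage of patients experiencing each type of adjudicated event by study completion". For the time to first primary event it adds "Event probabilities at 6-month intervals", again from Kaplan-Meier.

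The handling of death is explicit:

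- **Primary endpoint (SAP 4.7.1.1).** Patients with a non-CV death within 90 days of last contact and "without having had an earlier CV event will be censored at the time of death". If the non-CV death came more than 90 days after last contact, they are censored at that contact. Deaths of undetermined cause count as CV deaths.
- **CV death component (SAP 4.7.2).** Here "patients who do not die from CV causes will be censored at death from non-CV causes or last visit/phone contact".
- **Nonfatal MI, nonfatal stroke, coronary revascularization and unstable angina (SAP 4.7.2).** Here "patients who do not experience the event will be censored at death or last visit/phone contact", so CV deaths are censored as well.

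SAP 4.7.3 and 4.7.4 carry the same methods and date rules to the secondary endpoints and the tertiary time-to-event endpoints.

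Three other parts of the plan come close to the issue. The Li-Lagakos analysis (SAP 4.7.1.2 and 4.7.2) allows for death, but only when estimating treatment effects on recurrent events. iSAP 4.2.5 plans cumulative incidence plots for the control arm at the interim analyses and names no estimator. Two ranked secondary endpoints count all-cause death as an event, but they are different endpoints.

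**The concern.** Death is not ordinary censoring here. A patient lost to follow-up may still have an MI, whereas a patient who has died cannot. Kaplan-Meier treats both alike: it spreads the future risk of those censored over those still under observation. Its complement is then the risk in a population where the censored deaths do not happen, not the percentage of patients who experience the event. It can never fall below that percentage, and the gap widens as deaths accumulate over follow-up of up to 6.5 years.

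The interpretation is weakest for the nonfatal components. The censored deaths there include CV deaths, which share causes with MI and stroke, so independent censoring is hard to defend.

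What is at stake is the arm-level absolute risk in the report, which readers will take literally as the share of patients affected.

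**Working it through.** **Inputs from the documents.** Control arm: "A one-year event rate of 5.2% (hazard = 0.053) in the control arm is also assumed" (SAP 3.2). Effect: "A risk reduction corresponding to a hazard ratio of 0.85 (AMR101 vs. control) is assumed", giving a treated hazard of 0.85 × 0.053 = 0.045. About 3995 patients per arm (protocol 3.6). Accrual of 20/40/20/19/1% over 4.2 years, study end at 6.5 years, no dropout (SAP 3.2).

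**Inputs not in the documents, hence assumed.** Non-CV death at 0.3% to 2.0% per year. Each nonfatal component at 0.5% to 2.5% per year, with all-cause death at 0.5% to 3.0% per year.

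**The plan's own figures first.** The SAP states that "1612 events would be required to detect this hazard ratio with approximately 90% power with one-sided alpha-level at 2.5% and with two interim analyses". The Schoenfeld formula for a fixed design gives 4 × (1.960 + 1.282)² / (ln 0.85)² = 1592 events. With the iSAP Table 1 boundaries, 1612 events give power 0.897, as that table states. Exponential event times over the stated accrual give 1612 events at N = 7990 with the unrounded hazard −ln(1 − 0.052) = 0.0534, and 1601 with the rounded 0.053. The design figures reproduce.

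**Formulas.** With constant event hazard λ and competing-death hazard c:

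- One minus Kaplan-Meier: 1 − exp(−λt)
- Cumulative incidence: λ/(λ+c) × [1 − exp(−(λ+c)t)]
- Greenwood SE: exp(−λt) × √{ ∫₀ᵗ λ du / [n G(u) exp(−(λ+c)u)] }, where G(u) is the share of patients whose entry date allows at least u years of follow-up (10% at 6 years)

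**Worked case: control arm, 6 years, c = 0.01.** Kaplan-Meier: 1 − exp(−0.318) = 27.24%. Cumulative incidence: (0.053/0.063) × [1 − exp(−0.378)] = 0.8413 × 0.3148 = 26.48%. The overstatement is 0.76 points. With an SE of 1.02 points, that is 0.75 SE.

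**Primary endpoint at 6 years** (Kaplan-Meier: control 27.24%, treated 23.68%, difference 3.55 points before rounding)

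| Non-CV death per year (assumed, both arms) | Control, cumulative incidence | Overstatement, points (SE) | Treated, cumulative incidence | Difference between arms, points |
|---|---|---|---|---|
| 0.3% | 27.01% | 0.23 (0.23) | 23.48% | 3.53 |
| 0.5% | 26.86% | 0.38 (0.38) | 23.35% | 3.51 |
| 1.0% | 26.48% | 0.76 (0.75) | 23.02% | 3.46 |
| 1.5% | 26.11% | 1.13 (1.10) | 22.70% | 3.42 |
| 2.0% | 25.75% | 1.49 (1.43) | 22.38% | 3.37 |

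At 5 years and 1.0% per year the control figures are 23.28% against 22.73%. A simulation of 300 trials with the plan's accrual gave 23.28% against 22.73% at 5 years and 27.23% against 26.46% at 6 years.

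**Nonfatal components at 6 years**

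| Component hazard per year | All-cause death per year | Kaplan-Meier | Cumulative incidence | Overstatement, points (SE) |
|---|---|---|---|---|
| 0.5% | 0.5% | 2.96% | 2.91% | 0.04 (0.12) |
| 0.5% | 1.0% | 2.96% | 2.87% | 0.09 (0.23) |
| 1.0% | 2.0% | 5.82% | 5.49% | 0.33 (0.62) |
| 2.5% | 3.0% | 13.93% | 12.78% | 1.15 (1.42) |

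**Effect on the difference between arms.** For non-CV death of 0.5% to 2.0% per year in both arms, the 6-year difference falls by 0.05 to 0.18 points (0.03 at 0.3%). That is at most 0.13 of its SE.

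**The case against.** The strongest reply is that this is a matter of labelling. Kaplan-Meier and cumulative incidence answer different questions, observed counts stand beside the Kaplan-Meier figures, and nothing confirmatory depends on the choice. Several features also hold the competing hazard down for the primary endpoint: undetermined deaths count as CV events, and patients with a non-CVD illness expected to be fatal within 2 years are excluded. Non-CV deaths also show up in the total-mortality endpoints.

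Much of this stands. It limits the size of the problem and confines it to description. It does not remove it. The SAP names the quantity as a percentage of patients, and the planned estimator does not target that quantity. Crude counts do not supply it either, because with staggered entry a raw proportion mixes follow-up times. The 2-year exclusion covers only part of a follow-up that may last 6.5 years.

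Two stronger readings should be resisted. A reader might infer a fixed bias, say 0.7 to 1.3 standard errors. For the control-arm primary endpoint, that would need non-CV death of about 0.9-1.1% up to 1.8-2.2% per year, depending on the time point. The documents give no such rate, and rarer components mostly fall below 0.7. A reader might also infer that the efficacy test or the absolute benefit is distorted. The log-rank test and Cox model compare cause-specific hazards and are unaffected by how the percentages are estimated, and the table shows the difference between arms barely moving.

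**Conclusion.** The point holds as a correction to descriptive estimates. The direction is certain: with deaths censored, the stated percentages are at or above the true share of patients in each arm. The size is conditional. At 6 years it is about 0.2 to 1.5 points (0.2 to 1.4 SE) for the control-arm primary endpoint if non-CV death is 0.3% to 2% per year, and about 0.1 to 1.4 SE for components over the assumed rates. These figures rest on constant hazards, the plan's accrual and no dropout.

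The tests, hazard ratio, alpha, power and the 1612 events stand. The near-unchanged difference between arms assumes similar death rates in both. With 1.0% in control and 1.5% in the treated arm, it would be 26.48 − 22.70 = 3.78 points against 3.55 by Kaplan-Meier. Nothing in the documents suggests such an imbalance.

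**What to change.** In SAP 4.7.1.1, 4.7.2, 4.7.3 and the time-to-event part of 4.7.4:

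1. Report the event percentages, at 6-month intervals and at study completion, from the Aalen-Johansen cumulative incidence.
2. Treat as competing any death that is not itself part of the endpoint. That means non-CV death for the primary, key secondary and CV-death endpoints, any death for the nonfatal components and for revascularization or unstable angina alone, and any death other than a fatal MI or a fatal stroke for the fatal-or-nonfatal endpoints.
3. State whether a non-CV death more than 90 days after last contact is a competing event at the date of death or is censored at last contact as now. The first choice assumes no event in the unobserved gap. The second treats a known death as loss to follow-up.
4. Keep the stratified log-rank test and the Cox model. Keep Kaplan-Meier for endpoints that include all-cause death, and alongside for the curves if wanted.

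The cost is a few sentences in the SAP, a little more programming and slightly lower stated percentages. No new data are needed, because cause and date of death already drive the censoring rules, and no test changes.

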4.7.1.2 Other Sensitivity, Supportive, and Exploratory Analyses for the Primary Efficacy Endpoint

As a sensitivity analysis, patients who discontinue study drug prematurely will be censored for the composite endpoint analysis on the date of drug discontinuation. The primary analysis will be repeated using this censoring rule for the mITT population.

In the primary analysis, the date of first ECG indicative of a silent MI will be taken as the date for that silent MI. The following sensitivity analyses regarding this definition will be carried out both on the ITT and mITT populations:

1. Date of silent MI = Date of last normal ECG + 1; and
2. Date of silent MI = Mid-point between date of last normal ECG and date of first indicative ECG.

In the primary analysis, deaths with undetermined cause and without a preceding primary endpoint event constituent will be regarded as CV deaths. A sensitivity analysis where patients are censored for these cases will be carried out both on the ITT and the mITT populations.

Since the primary efficacy endpoint is a composite of five cardiovascular events, recurrence of such events within each patient is possible. For this reason, a supportive analysis using a Cox proportional-hazard with the counting-process formulation of Andersen and Gill (Andersen and Gill, 1982) will be carried out to model the recurrent cardiovascular events. Since death is a terminating event, the modified Wei-Lin-Weissfeld (WLW) method (Wei, Lin, and Weissfeld, 1989) for analysis of recurrent events in presence of death proposed by Li and Lagakos (Li and Lagakos, 1997) will also be carried out as a supportive analysis. Both analyses will be carried out for the ITT and mITT populations.

As an exploratory and supportive analysis, a stratified Cox proportional hazards model will be constructed for the primary endpoint to evaluate the treatment effect adjusting for important baseline covariates. Stratification variables will include CV risk category at baseline, use of ezetimibe at baseline, and geographical region (Westernized, Eastern European, and Asia Pacific countries). The model will include treatment and any of the following variables that are identified by a stepwise selection procedure:

- Gender;
- Age at baseline (<65 or ≥65 years);
- Race (White and non-White);
- Presence/absence of diabetes at baseline;
- Baseline LDL-C (by tertile);
- Baseline HDL-C (by tertile);
- Baseline non-HDL-C (by tertile);
- Baseline TG (by tertile);
- Baseline hs-CRP (≤ 3 mg/L and >3 mg/L);
- Baseline Apo B (by tertile);
- Baseline RLP-C (by tertile);
- Hopkins calculated LDL-C at baseline (by tertile);
- Waist/height ratio at baseline; and
- Waist circumference at baseline.

The minimum p-value to enter will be 0.05 and selected variables with $p < 0.10$ will remain in the model. The hazard ratio (HR), 95% confidence interval (CI) and p-value comparing the two treatment groups, and the hazard ratio, 95% CI and p-value for each covariate in the final model will be presented.

